3 OBJECTIVES

3.1 STUDY OBJECTIVES

We will compare two interventions to improve the cardiovascular/hemodynamic stability of HD care by pursuing the following specific aims:

- **Aim 1** Conduct a cluster-randomized controlled trial (CRCT) to test and compare the effects of the above HD facility-level interventions on the primary outcome of dialysis session stability over an intervention period of 24 weeks and a post-intervention follow-up period of 12 weeks.
- **Aim 2** Test and compare the effects of the two HD facility-level interventions on secondary patient-centered clinical outcomes, including: patient symptoms, fluid adherence, dialysis adherence, quality of life, hospitalizations and mortality over the same timeframe.
- **Aim 3** Identify factors associated with successful implementation of the interventions, and ways in which implementation may influence intervention effectiveness.

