7 STUDY SCHEDULE

The active intervention will begin in sets of four clinics at a time, each randomized to one of four treatments. See Schedule of Events in Appendix A for staggered roll out dates. The study coordinator will contact each clinic manager by phone -7 to -4 months from data collection start. The Study Coordinator helpline will be available during the preparation and enrollment periods, one month prior to data collection, in order to assist with patient or clinic questions. The study coordinator will schedule digital meetings for each provider education clinic in intervention weeks 1-3 to conduct the first online training and in weeks 4-6 to conduct the second online

training. Study coordinator(s) will be available by phone for questions or concerns throughout the study. See the Schedule of Events for an overview of the study schedule.

The patient activation intervention should take 5-6 weeks on average to complete. We anticipate staggered participation of patients in the patient activation intervention due to limits on the number of tablet computers and the number of peer mentors.

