Table 7 above shows the statistical power for a range of SD, ICC, and Control vs. Intervention differences (D). Power is around 80% or higher to detect differences of 0.9 or higher for all cases except SD=2, ICC=0.2. In this worst case, we still have 68% power to detect a difference of 1.0 between intervention and control groups. A difference of 0.8 to 1.0 would be clinically meaningful, and is much smaller than a SD by either assumption (effect size range from 0.40 to 0.67, all considered a moderate effect size). In summary, the recovery time outcome measure is well powered to detect meaningful effects.

(c) Patient Symptoms – Symptom Burden Measure

The Patient Symptom Burden measure will combine symptom frequency and severity for each of the following symptoms that are often indicative of IDH, if they occur during or after the dialysis session (not pre-dialysis): nausea, vomiting, abdominal pain, dizziness, muscle cramps, headache, chest pain, shortness of breath, palpitations, diaphoresis, and blurred vision (as listed in the Chair-side symptom module). Although not yet fully developed, we assume that the range of the scale will be 0-100. As above, we assume 20 facilities, and anticipate an average of 60 study patients per facility.

Each patient's data over the 24-week intervention period will be averaged and used as their individual Symptom Burden (SB) mean. We will use the group-level means (the average of the patient-level means) for comparing the intervention and control groups.

[figure not shown]
In Table 7, we assess the power to detect various differences between the intervention mean and the control mean. For example, a SB of 15 in the control group and 10 in the intervention group would be a difference of 5. We assume an intra-class correlation coefficient (ICC, which measures how strongly patients are similar within center and differ between facilities) of either 0.1 or 0.2 (lower ICC results in higher power). We assume a SB standard deviation (SD) among patients of 10, and a 2-sided significance level of 0.05.

Table 8 - Entries are the statistical power for a standard deviation (SD) of 10, intraclass correlation coefficient (ICC) of 0.1 and 0.2, and control vs. intervention difference of 4, 5, and 6 (on a 0-100 scale). Power values ≥ 0.80 are in boldface.		
Control vs. Intervention Difference	ICC=0.1	ICC=0.2
4	0.75	0.49
5 (Effect Size=0.5)	0.91	0.68
6	0.98	0.83

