Aim 2. Test and compare the effects of the two HD facility-level interventions on secondary patient-centered clinical outcomes, including: patient symptoms, fluid adherence, dialysis adherence, quality of life, hospitalizations and mortality over the same timeframe.

Aim 2 incorporates six outcome measures: (1) patient symptoms (including a patient burden measure, dialysis recovery time, and proportion of sessions with each symptom), (2), fluid adherence (inter-dialytic weight gain), (3) dialysis adherence, (4) quality of life, (5) hospitalization (all-cause and by specific cause), and (6) mortality (all-cause and by specific cause), with will be analyzed at the individual level and summarized at the facility level. Each

will use a model format appropriate to the outcome type, but will otherwise follow the model strategy, including the secondary analyses, described for Aim 2 above. This includes censoring of patient data while they are at another facility. The fluid adherence (Interdialytic weight gain), symptom and quality of life analyses, based on continuous outcome measures, will be carried out using mixed models (the MIXED procedure of SAS). Note that the quality of life analyses will be based on data from two time points, one before intervention and one during intervention, rather than session-specific data as analyzed for the other outcomes. Analyses of missed or shortened HD sessions will employ logistic regression for longitudinal data, as in Aim 2. Analyses of hospitalization and mortality will use logistic regression for individual level data. As part of these models, we will test IDH-related variables (e.g., recent IDH, frequency of IDH in the past month) as potential predictors. In each case, the appropriate regression diagnostics will be used to assess model fit.

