In both Aims 1 and 2, the primary results will be based on the treatment effects tested in the initial models described for CRCTs with pre-planned covariates. Depending on the specific outcome, covariate adjustment for these analyses will include: (1) patient demographics (age, race, ethnicity, sex, employment, literacy, education level, language spoken), (2) time since first dialysis, (3) cause of ESRD, (4) treatment history, (5) total transplants, (6) vascular access type, (7) patient laboratory data (serum phosphorous, dialysis adequacy, anemia management (hemoglobin), iron indices (ferritin, serum Iron), mineral metabolism indices (calcium, phosphate, PTH)); (8) comorbidity index; (9) individual comorbidities and comorbidities in combination, including COVID-19; (10) patient's heart rate variability for the whole session or up until IDH occurs (if IDH occurs) (based on variability in heart rate (HR) during dialysis session (Difference between the highest and lowest heart rates, standard deviation of the heart rate measures, the square root of the mean squared differences of successive heart rate measures)); and (11) patient medications (prescriptions medications administered outside of center or in-center (including ESA prescription, iron, antibiotics and vitamin D analog)). Intent-to-treat analyses will be carried out, which means that any deviations from the randomized interventions will not be taken into account in the primary test of treatment effects. Additionally, we will conduct as-treated analyses for the peer mentoring intervention whereby only patients who received peer mentoring are compared to patients in the other treatment arms, with adjustment for the same factors as in the intent-to-treat analyses. The small number of facilities (20) will preclude post-hoc adjustment for facility non-compliance with the interventions.

Heterogeneity of Treatment Effect Analyses (Moderation). As with the primary outcome analyses, the following potential moderators will be assessed: 1) patient demographics, including age, race, ethnicity, literacy, and education level; (2) comorbidities; and (3) heart rate variability.

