FMCNA	
Report on patient peer mentoring program completion, transferred from Peer Mentoring Management System by UMSI Principal Investigator and/or Study Coordinators with FKC ID2, which FMCNA will match to FKC ID1
 
Report on patient peer mentoring completion send to UM-KECC using FKC ID1
	
Number of Peer Mentoring Sessions Completed
 
Peer Mentoring Start Date
 
Peer Mentoring Stop Date
	
FMCNA Data Analysts
 
UM-KECC Programmer/Analysts
 
Co-PI [name], Biostatisticians

Study team	
Patient Training Fidelity Checklist
 
Completed by UMSI study staff following technology training calls to patients who have joined peer mentoring
 
Data transferred from paper form to Excel or Word format
	
Items discussed during tech training call
 
Major questions or issues outside of fidelity checklist
 
“25.1_PM_Recruitment_and_Retention_Procedure”
	
[name]
 
UMSI Project Coordinators

Study team	
Patient Technology Training Records
 
Completed by UMSI study staff to track number of technology training calls without identifying patient names
 
Stored on UMSI secure server and PMMS
	
Whether patients in the peer mentoring program accept or decline a tech training call
 
“Training Records” tab of “Tech Calls” document
	
[name]
 
UMSI Project Coordinators
 
National Kidney Foundation Project Coordinators
 
[name], University of California at Irvine (Co-Investigator)
 
Paid Developer at University of California at Irvine, supervised by [name]

Study team	
Technology Support Records
 
Completed by UMSI study coordinators to track the technical support provided to clinics and members of the
	
Major questions or items discussed from calls to the study helpline
 
Who contacted UMSI (mentee, mentor, clinic staff)
	
[name]
 
UMSI Project Coordinators

	
peer mentoring program, without identifying patient or provider names
 
Stored on UMSI secure server and PMMS
	
Date and time of call
 
“Tech support log” tab of “Tech Calls” document
	
National Kidney Foundation Project Coordinators
 
[name], University of California at Irvine (Co-Investigator)
 
Paid Developer at University of California at Irvine, supervised by [name]

Provider education intervention			

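### The as-treated analyses set no time zero and do not say how time before mentoring is handled, so under the stated logistic model mortality (and, less directly, hospitalization) is biased towards mentoring even if mentoring does nothing

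*Combined protocol and SAP*

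**What the plan says.** Section 11.4 plans as-treated analyses under Aim 1 and again in the text covering Aims 1 and 2, "whereby only patients who received peer mentoring are compared to patients in the other treatment arms". The covariate set does not change, since the comparison is to be made "with adjustment for the same factors as in the intent-to-treat analyses". Section 11.4 does not define received, set a time zero, or name a landmark, delayed entry or time-varying exposure.

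For the outcomes most affected, section 11.4 says: "Analyses of hospitalization and mortality will use logistic regression for individual level data". The timeframe is that of Aim 1 (section 3.1): "over an intervention period of 24 weeks and a post-intervention follow-up period of 12 weeks". For symptom burden, section 11.2 says each patient's "data over the 24-week intervention period will be averaged"; recovery time is handled in the same way.

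Mentoring does not start for everyone at once. Section 7 says: "We anticipate staggered participation of patients in the patient activation intervention", because tablets and mentors are limited. Section 5.4.1 draws patients in succession, replaces those who decline, and adds patients who enter the facility in weeks 1-18.

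Timing data exist. Section 14.5 (Limited Data Set) says the as-treated analyses need to know when mentoring was received. Table 9 in section 12 and Table 11 in section 14.5 send the "Peer Mentoring Start Date" to the analysts. No section says how that date enters a model.

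**The concern.** Receiving mentoring is a status acquired after baseline. Someone who dies or leaves the clinic before starting can never be classed as mentored, whereas a comparison patient who dies in the same weeks counts as a death. A yes/no logistic model over a fixed window has no entry time, and none of the listed covariates corrects this. The bias would arise even if acceptance were random. It is therefore separate from the tendency of healthier patients to volunteer, which section 2.2.2 recognizes.

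Hospitalization is affected less directly. A patient hospitalized before mentoring can still be mentored later, so the bias acts through admissions that end in death or departure or that prevent a start.

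For session outcomes, sessions before mentoring count as treated and dilute any real effect.

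At stake is the analysis meant to show what mentoring does when it is received: it could report a survival benefit with no effect present.

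**Working it through.** The documents give no figure for as-treated mortality, so there is none to reproduce.

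**Inputs**
- Annual mortality 17.5% (section 2.1.3); 15-20% in section 9.3.
- Window 24 + 12 = 36 weeks (section 3.1).
- Mentored: 30 x 10 = 300 (section 5).
- Comparators: 600 in the facilities without patient activation (Table 1, section 4.1). This is one reading of the other treatment arms.
- Start weeks: not given, so assumed uniform over weeks 1-8, 2-12 or 2-18.
- No true effect and a constant hazard.

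**Risks**
- Weekly hazard h = -ln(1 - 0.175)/52 = 0.00370.
- Comparators: 1 - exp(-36h) = 12.5%, odds 0.1425, or 37.4 deaths per 300.
- A patient starting in week s is known to be alive at s, so the risk is 1 - exp(-h(36 - s)), averaged over start weeks.

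| Assumed starts | Mean start week | Risk if mentored | Deaths per 300 | Null OR | False-positive rate |
|---|---|---|---|---|---|
| Weeks 1-8 | 4.5 | 11.0% | 33.0 | 0.87 | 8-10% |
| Weeks 2-12 | 7 | 10.2% | 30.5 | 0.80 | 15-17% |
| Weeks 2-18 | 10 | 9.2% | 27.6 | 0.71 | 29-31% |

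Example for weeks 2-18: odds 0.0918/0.9082 = 0.101, and 0.101/0.1425 = 0.71. The standard error of the log OR is sqrt(1/27.6 + 1/272.4 + 1/74.8 + 1/525.2) = 0.235. So z = ln(0.71)/0.235 = -1.46, and the chance of passing -1.96 is about 31%. Simulation and normal approximation differ slightly, hence the ranges. Annual mortality of 15% or 20% leaves this OR at 0.71.

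**Late entry of comparators.** Suppose 15% of comparators enter uniformly over weeks 4-16 (assumed; section 5.4.1 expects 15-20% turnover over 11 months). Their risk is about 9.2%, so the comparator risk becomes 0.85 x 12.5% + 0.15 x 9.2% = 12.0%. The null ORs become about 0.91, 0.83 and 0.74. For weeks 2-18 the false-positive rate falls to about 22-24%.

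**Clustering.** With an assumed intraclass correlation of 0.01-0.02 for death, the weeks 2-18 rate is roughly 20-24%, without late entry.

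**With time at risk aligned.** In a simulation with starts in weeks 2-18, mentored patients were counted only from their own start, in a person-time rate ratio. The null rate ratio was 0.99 with 5.0% false positives, against an OR of 0.70 and 30% for the fixed-window logistic model.

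**Session outcomes.** The pre-mentoring share of the window is the mean start week divided by its length: 4.5/36, 7/36 and 10/36, or 13%, 19% and 28%. Over the 24-week averaging window it is 19%, 29% and 42%. If the effect begins when mentoring begins, the estimate shrinks by about that share.

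**The case against.** A reader might infer that the plan counts mentored patients from the start of the intervention period. No section says so. The text is silent on time zero, and section 14.5 ties the timing of mentoring to these very analyses. That stands. The point is that the stated model and timeframe make no use of the date, so following the text as written gives the bias.

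A reader might also treat week 18 as the end of a known start distribution. In section 5.4.1 it is the cut-off for newcomers' entry to the facility. Starts could be mostly early, and then the bias is small: OR 0.87, or about 0.91 with late-entering comparators.

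Nor are all comparators at risk from day one. Sections 4.1 and 7.2 enrol new patients at every facility until 8 weeks before the intervention period ends. This reduces the bias but does not remove it.

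A 24-week window would give a more extreme OR (0.57 for weeks 2-18), but the stated mortality timeframe is 24 + 12 weeks.

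Survival bias should not be read into the main analysis of intradialytic hypotension. The linear model keeps only patients with at least 60 sessions, in both groups, which largely equalises survival. The remaining error is dilution, which is conservative.

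Finally, intent-to-treat is primary, section 5.4.2 calls the as-treated analyses supplementary, and the trial is not powered for death as a primary outcome. All of this limits the consequence.

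**Conclusion.** The concern holds as a gap in the as-treated specification that gives a biased result under the model the plan names. With no true effect, mortality favours mentoring by an OR of about 0.87 to 0.71, depending on start weeks that the documents do not give. False-positive rates run from roughly 8-10% to 29-31% before clustering, and somewhat lower once late entry of comparators is allowed for. These figures assume a constant hazard, 300 mentored patients and 600 comparators. Hospitalization is exposed through the same mechanism, but its size was not computed. For intradialytic hypotension and the other session outcomes the main error is dilution. The primary intent-to-treat results are unaffected. The as-treated specification should be corrected before analysis.

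**What to change.** In both as-treated paragraphs of section 11.4, define received and time zero.

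- **Mortality and hospitalization:** replace the fixed-window logistic model with a person-time or survival model. Each patient enters at their own study entry date, and mentoring is time-varying from the Peer Mentoring Start Date, so earlier weeks count as unmentored. Alternatively, use a landmark: classify patients alive and at the clinic at a fixed week, and count only later outcomes, alike in mentored and comparison patients. Moving the clock for mentored patients alone would not help, because the logistic model would then compare a shorter window with a longer one.
- **Session outcomes:** for intradialytic hypotension, code mentoring as time-varying by session in the all-patient longitudinal GLIMMIX model already planned in section 11.4, with study week in the model. Code other session-level outcomes in the same way in their longitudinal models. Do not put a week-18 landmark on the 60-session linear model: at three sessions a week, the remaining 18 weeks give 54 sessions, so no one on that schedule would qualify.

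The cost is SAP text and programming, since the dates are already transferred. A landmark also loses the events before it. The analysis stays supplementary to intent-to-treat, and selection of healthier acceptors remains a separate limitation.

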12 SOURCE DOCUMENTS AND ACCESS TO SOURCE DATA/DOCUMENTS

Table 9 – Sources of Materials and Access to Materials			
Patient activation intervention using peer mentoring			
Source	Data Collection Mode	Variables (examples)	Who will have access
FMCNA	Electronic health record (EHR) and session data for each dialysis session	Personal health information (PHI) (includes demographic information, comorbidities, medications, lab tests, dialysis session data, Quality of life survey)	FMCNA will transfer a limited data set using unique FKC identifier for each patient UM-KECC Programmer/Analysts Co-PI [name], Biostatisticians
National Kidney Foundation	Peer Mentoring Management System (PMMS) stored on secure, HIPAA-compliant server at the University of Michigan Medical School	Peer Mentor demographics (age, gender, race ethnicity, education) Mentor-mentee matches Scheduled peer mentoring sessions Average number of mentoring sessions completed per patient Patient retention rates across all five peer mentoring sessions	National Kidney Foundation Principal Investigator, Study Coordinators and Postdoctoral Research Fellow at University of Michigan School of Information University of California at Irvine staff (system developers)
National Kidney Foundation	Patient Intervention Completion Data – Peer Mentoring live sessions Peer mentoring videoconference completion data via VSee stored in Peer Mentoring Management System (PMMS) with non-identifying patient login	Whether session was completed Number of people in session Session length Average peer mentoring session length	National Kidney Foundation Principal Investigator, Study Coordinators and Postdoctoral Research Fellow at University of Michigan School of Information University of California at Irvine staff (system developers)
Study team	Patient Intervention Completion Data – Tablet-based Educational Modules - each patient will be given a	Education module completion rates by topic and section	Principal Investigator, Study Coordinators and Postdoctoral Research Fellow at University of

	
unique login ID at the beginning of the study, and this will be used to track usage of the educational modules; this log in ID will be identifiable only to study coordinators through the Peer Mentoring Management System (PMMS)
 
No PHI will be stored on the tablets at any time
	
Quiz completion rates
 
Average time spent on each educational module section
 
Usability: (1) time spent on each page; (2) number of abandoned checklist sessions, videoconferencing or patient education module sessions; (3) pages and click-through patterns preceding abandonment.
	
Michigan School of Information
 
University of California at Irvine staff (system developers)

National Kidney Foundation	
Checklist of peer mentoring training topic coverage
 
Data transferred to Excel or Word format
	
Fidelity of the peer mentoring training
 
Proportion of training session in which all elements completed
	
National Kidney Foundation
 
Principal Investigator, Study Coordinators and Postdoctoral Research Fellow at University of Michigan School of Information

National Kidney Foundation	
Checklists of topic coverage and behavior change technique implementation
 
Data transferred to Excel or Word format
	
Fidelity of the peer mentoring intervention
 
Proportion of peer mentoring sessions in which all session components completed
 
Mentor-specific peer mentoring completion rates
	
National Kidney Foundation
 
Principal Investigator, Study Coordinators and Postdoctoral Research Fellow at University of Michigan School of Information

National Kidney Foundation	Survey on Qualtrics Platform	Peer Mentor satisfaction with peer mentoring	
National Kidney Foundation
 
Principal Investigator, Study Coordinators and Postdoctoral Research Fellow at University of Michigan School of Information

National Kidney Foundation	Survey on Qualtrics Platform	Patient mentee satisfaction with peer mentoring (see attached documents: Peer Mentee Satisfaction Survey and Peer Mentor Satisfaction Survey)	
National Kidney Foundation
 
Principal Investigator, Study Coordinators and Postdoctoral Research Fellow at University of Michigan School of Information

			Michigan School of Information
FMCNA	
Report on patient peer mentoring program completion, transferred from Peer Mentoring Management System by UMSI Principal Investigator and/or Study Coordinators with FKC ID2, which FMCNA will match to FKC ID1
 
Report on patient peer mentoring completion send to UM-KECC using FKC ID1
	
Number of Peer Mentoring Sessions Completed
 
Peer Mentoring Start Date
 
Peer Mentoring Stop Date
	
FMCNA Data Analysts
 
UM-KECC Programmer/Analysts
 
Co-PI [name], Biostatisticians

Study team	
Patient Training Fidelity Checklist
 
Completed by UMSI study staff following technology training calls to patients who have joined peer mentoring
 
Data transferred from paper form to Excel or Word format
	
Items discussed during tech training call
 
Major questions or issues outside of fidelity checklist
 
“25.1_PM_Recruitment_and_Retention_Procedure”
	
[name]
 
UMSI Project Coordinators

Study team	
Patient Technology Training Records
 
Completed by UMSI study staff to track number of technology training calls without identifying patient names
 
Stored on UMSI secure server and PMMS
	
Whether patients in the peer mentoring program accept or decline a tech training call
 
“Training Records” tab of “Tech Calls” document
	
[name]
 
UMSI Project Coordinators
 
National Kidney Foundation Project Coordinators
 
[name], University of California at Irvine (Co-Investigator)
 
Paid Developer at University of California at Irvine, supervised by [name]

Study team	
Technology Support Records
 
Completed by UMSI study coordinators to track the technical support provided to clinics and members of the
	
Major questions or items discussed from calls to the study helpline
 
Who contacted UMSI (mentee, mentor, clinic staff)
	
[name]
 
UMSI Project Coordinators

	
peer mentoring program, without identifying patient or provider names
 
Stored on UMSI secure server and PMMS
	
Date and time of call
 
“Tech support log” tab of “Tech Calls” document
	
National Kidney Foundation Project Coordinators
 
[name], University of California at Irvine (Co-Investigator)
 
Paid Developer at University of California at Irvine, supervised by [name]

Provider education intervention			
FMCNA	Electronic health record (EHR) and session data for each dialysis session	
Personal health information (PHI) (includes demographic information, comorbidities, medications, lab tests, dialysis session data, Quality of life survey)
	
FMCNA will transfer a limited data set using unique FKC identifier for each patient
 
UM-KECC Programmer/Analysts
 
Co-PI [name], Biostatisticians

Study team	Practice Patterns Survey for (1) Medical Directors and (2) Nurse Managers delivered before and after intervention via Qualtrics Platform	
Practices for assessing patient estimated dry weight at facility
 
Practices for managing intradialytic weight gain at facility
 
Facility policies regarding fluid removal and ultrafiltration rates
	
Principal Investigator, Study Coordinators and Postdoctoral Research Fellow at University of Michigan School of Information
 
UM-KECC Programmer/Analysts
 
Co-PI [name], Biostatisticians

Study team	Provider team training fidelity checklists – completed on paper and transferred to Excel	
Average proportion of training elements completed
 
Proportion of training sessions in which all training elements completed
	
Principal Investigator, Study Coordinators and Postdoctoral Research Fellow at University of Michigan School of Information
 
Co-Investigator [name]

Dialysis facilities	Checklist Completion Data from Checklist application on tablet computer used at facility with facility-level login	Checklist completion rate by facility over specific time points	Principal Investigator, Study Coordinators and Postdoctoral Research Fellow at University of

	
only; no tracking of individual staff
 
Checklist completion data stored in database on secure, HIPAA-compliant server at the University of Michigan Medical School
	
Proportion of checklist sessions in which patients are identified as being at risk of IDH
 
Prevalence of reasons why patients were identified as being at risk of IDH
	
Michigan School of Information
 
University of California at Irvine staff (system developers)

Study team	
Online training attendance records - Paper form lists number in attendance by role only
 
FMCNA clinics to share attendance by role in digital form via secure FMCNA email
 
Data from paper form transferred to Excel or Word format and stored on secure research server at the University of Michigan School of Information (UMSI)
	
Proportion of staff by role who completed each training session, tracked by facility
	
Principal Investigator, Study Coordinators and Postdoctoral Research Fellow at University of Michigan School of Information
 
Co-Investigator [name]

FMCNA	
Completion of training in learning management system
 
FMCNA shares training completion reports via SharePoint
 
Data transferred to Excel or Word format and stored on secure research server at the University of Michigan School of Information (UMSI)
	
Proportion of staff by role who completed each training session, tracked by facility
	
Principal Investigator, Study Coordinators and Postdoctoral Research Fellow at University of Michigan School of Information
 
Co-Investigator [name]

Study team	
Field Notes from Meetings tracked by facility ID; will include participant IDs which refer to facility and professional role (e.g., dietitian, NP)
 
Data will be stored in a Word Processing Program – Word and a Qualitative Data
	
Identify and explain types of implementation barriers and facilitators
 
Use qualitative analyses as supplementary explanations as we seek to explain the results of the trials, especially if there are differences in effectiveness
	
Principal Investigator, Study Coordinators and Postdoctoral Research Fellow at University of Michigan School of Information
 
Co-Investigator [name]

	
Analysis Software package (e.g., NVivo)
 
Files will be stored on a secure research server at the University of Michigan School of Information (UMSI)
	
between facilities implementing the same interventions
	

Note: data in the above table have been compiled based on the attached data flow diagram and the following attached documents: (1) implementation assessment plan; (2) peer mentor data relinking plan, (3) provider training fidelity checklists; (4) peer mentoring fidelity checklists; (5) peer mentee satisfaction survey; (6) peer mentor satisfaction survey; (7) practice patterns survey for Medical Directors; (8) practice patterns survey for Nurse Managers; and (8) HIPAA compliance of Dialysafe Tools; and (9) Data elements list.

See attached data use agreement for use of data from FMCNA and Study Facilities.

